9.0 Adverse Events List and Reporting Requirements

9.1 Adverse event list for daunorubicin

Acute myelosuppression is the dose limiting side effect, with the greatest effect on the granulocytic series. In addition, daunorubicin causes alopecia, and nausea and vomiting in a significant number of patients treated. Extravasation of daunorubicin can cause severe local tissue necrosis. There is increased potential for cumulative-dose-related cardiomyopathy with congestive heart failure.

9.2 Adverse event list for cytarabine (CYTOSAR)

Conventional Dose Therapy Table 1 - Adverse Reactions (with conventional dose therapy): The reported adverse reactions are listed below by MedDRA System Organ Class and by frequency. Frequencies are defined as: Very common (>10%), Common (>1%, ≤10%), Uncommon (>0.1%, ≤1%), Rare (>0.01%, ≤0.1%), and Frequency not known (cannot be estimated from available data).	
Blood and Lymphatic System Disorders:	
Very common	Bone marrow failure, thrombocytopenia, anaemia, anaemia megaloblastic, leukopenia, reticulocyte count decreased
Frequency not known	Bleeding (all sites)
Cardiac Disorders:	
Frequency not known	Pericarditis
Eye Disorders:	
Frequency not known	Conjunctivitis ^a

**CYTARABINE PLUS CONTINUOUS INFUSION DAUNORUBICIN, WITH CARDIAC
MRI MONITORING, INDUCTION THERAPY FOR ADULTS WITH ACUTE MYELOID
LEUKEMIA; A FEASIBILITY STUDY**

Wake Forest Baptist Comprehensive Cancer Center (WFBCCC) CCCWFU 22616

Gastrointestinal Disorders:	
Very common	Stomatitis, mouth ulceration, anal ulcer, anal inflammation, diarrhea, vomiting, nausea, abdominal pain
Frequency not known	Bowel necrosis, Pancreatitis, oesophageal ulcer, oesophagitis
General Disorders and Administration Site Conditions:	
Very common	Pyrexia
Frequency not known	Chest pain, injection site reaction ^b
Hepatobiliary Disorders:	
Very common	Hepatic function abnormal
Frequency not known	Jaundice
Infections and Infestations:	
Very common	Sepsis, pneumonia, infection ^c
Frequency not known	Injection site cellulitis
Immune System Disorders:	
Frequency not known	Anaphylactic reaction, allergic oedema
Investigations:	
Very common	Biopsy bone marrow abnormal, blood smear test abnormal
Metabolism and Nutrition Disorders:	
Frequency not known	Decreased appetite
Musculoskeletal, Connective Tissue and Bone Disorders:	
Very common	Cytarabine syndrome
Nervous System Disorders:	
Frequency not known	Neurotoxicity, neuritis, dizziness, headache
Renal and Urinary Disorders:	
Frequency not known	Renal impairment, urinary retention
Respiratory, Thoracic and Mediastinal Disorders:	
Frequency not known	Dyspnoea, oropharyngeal pain

^a may occur with rash and may be hemorrhagic with high dose therapy

^b pain and inflammation at subcutaneous injection site

^c may be mild, but can be severe and at times fatal

High Dose Therapy

Severe and at times fatal CNS, GI and pulmonary toxicity (different from that seen with conventional therapy regimens of CYTOSAR(cytarabine) has been reported following high dose schedules (2.0 g to 3.0 g/m² given every 12 hours for 12 doses). **Table 2: Adverse Reactions (with High Dose Therapy):** The reported adverse reactions are listed below by MedDRA System Organ Class and by frequency. Frequencies are defined as: Very common (>10%), Common (>1%, ≤10%), Uncommon (>0.1%, ≤1%), Rare (>0.01%, ≤0.1%), and Frequency not known (cannot be estimated from available data).

Cardiac Disorders:

Frequency not known	Cardiomyopathy ^a
---------------------	-----------------------------

**CYTARABINE PLUS CONTINUOUS INFUSION DAUNORUBICIN, WITH CARDIAC
MRI MONITORING, INDUCTION THERAPY FOR ADULTS WITH ACUTE MYELOID
LEUKEMIA; A FEASIBILITY STUDY**

Wake Forest Baptist Comprehensive Cancer Center (WFBCCC) CCCWFU 22616

Eye Disorders:	
Very common	Corneal disorder
Frequency not known	hemorrhagic conjunctivitis ^b
Gastrointestinal Disorders:	
Common	Necrotizing colitis
Frequency not known	Gastrointestinal necrosis, gastrointestinal ulcer, pneumatosis intestinalis, peritonitis
Hepatobiliary Disorders:	
Frequency not known	Liver injury, hyperbilirubinaemia
Infections and Infestations:	
Very common	Sepsis
Frequency not known	Liver abscess
Nervous System Disorders:	
Very common	Cerebral disorder, cerebellar disorder, somnolence
Frequency not known	Coma, convulsion, peripheral motor neuropathy, peripheral sensory neuropathy
Psychiatric Disorders:	
Frequency not known	Personality change ^c
Respiratory, Thoracic and Mediastinal Disorders:	
Very common	Acute respiratory distress syndrome, pulmonary oedema
Skin and Subcutaneous Tissue Disorders:	
Common	Skin exfoliation,

^aWith subsequent death
^b may be prevented or diminished by prophylaxis with a local corticosteroid eyedrop
^c Personality change was reported in association with cerebral and cerebellar dysfunction.

Peripheral motor and sensory neuropathies after consolidation with high-dose CYTOSAR, daunorubicin, and asparaginase have occurred in adult patients with acute non lymphocytic leukemia. Patients treated with high-dose CYTOSAR should be observed for neuropathy since dose schedule alterations may be needed to avoid irreversible neurologic disorders.

Corneal toxicity consisting of ocular pain, tearing, foreign-body sensation, photophobia and blurred vision has been reported.

Rarely, severe skin rash, leading to desquamation has been reported. Complete alopecia is more commonly seen with high dose therapy than with standard CYTOSAR treatment programs.

If high dose therapy is used, do not use a diluent containing benzyl alcohol.

CYTARABINE PLUS CONTINUOUS INFUSION DAUNORUBICIN, WITH CARDIAC
MRI MONITORING, INDUCTION THERAPY FOR ADULTS WITH ACUTE MYELOID
LEUKEMIA; A FEASIBILITY STUDY

Wake Forest Baptist Comprehensive Cancer Center (WFBCCC) CCCWFU 22616

Intermediate dose therapy

A diffuse interstitial pneumonitis without clear cause that may have been related to Cytosar was reported in patients treated with experimental intermediate doses of CYTOSAR (1 gm/m²) with and without other chemotherapeutic agents (meta-AMSA, daunorubicin, VP-16).

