6.1 Treatment Administration

Treatment will be administered on an inpatient basis. Reported adverse events and potential risks are described in Section 9. No investigational or commercial agents or therapies other than those described below may be administered with the intent to treat the patient's malignancy.

Agent	Dose	Route	Schedule	Cycle Length
Induction				
Cytarabine	100 mg/m ² /day	IV infusion	Days 1-7	14 days
Daunorubicin	60 mg/m ² /day	IV infusion	Days 1-3	
Re-induction (if needed)				
Cytarabine	100 mg/m ² /day	IV infusion	Days 1-5	14 days
Daunorubicin	60 mg/m ² /day	IV infusion	Days 1-2	
Consolidation (up to 3 cycles, or up to 4 cycles for CBF AML)				
Cytarabine	<60 yrs: 3,000 mg/m ² /day ≥ 60 yrs: 1,500 mg/m ² /day	IV infusion over 3 hours, every 12 hours	Days 1,3,5	≥ 28 days

Induction: This study regimen will follow the standard 7+3 regimen of cytarabine and daunorubicin, with the modification of daunorubicin administered as continuous infusion rather than bolus. Baseline troponin I, full 3D ECHO, and MRI without contrast will be performed prior to treatment.

For troponin determination, the study will use either the TnI-Ultra™ assay, Siemens, Munich Germany or the Beckman Coulter Access 2 AccuTnI+3 assay for detection of troponin I. While the assays are comparable, every effort will be made to test all samples on the current Institutional standard troponin I testing platform (TnI-Ultra assay, Siemens). If the TnI-Ultra assay becomes unavailable either because of changing Institutional standards or product availability the Beckman Coulter Access 2 AccuTnI+3 assay will be utilized. The brand of assay and results will be recorded for each test on the Cardiac Function Worksheet.

Patients will have a bone marrow aspirate and biopsy on day 14 (± 2 days).

Re-induction: A second induction course may be given if the day 14 bone marrow aspirate and biopsy shows bone marrow cellularity as $\geq 10\%$ and $> 5\%$ leukemic blasts. Those requiring re-induction will undergo a limited ECHO with strain measures prior to treatment. This abbreviated cycle will consist of cytarabine on days 1-5 and daunorubicin on days 1 and 2, with a troponin I measure on day 3 and a bone marrow biopsy on day 14 (± 2 days). Patients not achieving a remission after 2 induction attempts will be removed from study.

CYTARABINE PLUS CONTINUOUS INFUSION DAUNORUBICIN, WITH CARDIAC
MRI MONITORING, INDUCTION THERAPY FOR ADULTS WITH ACUTE MYELOID

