LEUKEMIA; A FEASIBILITY STUDY

Wake Forest Baptist Comprehensive Cancer Center (WFBCCC) CCCWFU 22616

Patients without bone marrow involvement at diagnosis will receive a second induction course if they have not cleared their soft tissue disease by day 14 (± 2 days).

If cellularity is $<10\%$ on day 14, a repeat bone marrow biopsy should be obtained as clinically indicated. Treatment response will be evaluated once ANC $>1,000 / \mu\text{L}$ and platelets $\geq 100,000 / \mu\text{L}$, but no later than day 42. If peripheral blood counts are inadequate (ANC $<1,000 / \mu\text{L}$, platelets $<100,000 / \mu\text{L}$) at the time of this bone marrow aspirate and biopsy, a repeat bone marrow aspirate and biopsy must be obtained to document complete remission at the time of peripheral blood count recovery (ANC $\geq 1,000 / \mu\text{L}$, platelets $\geq 100,000 / \mu\text{L}$) if > 1 week after "day 42" bone marrow study.

Physicians should consider earlier bone marrow exams in patients whose peripheral blood counts are not recovering or recovering sluggishly, as well as in patients whose day 14 bone marrow was suspicious for residual leukemia.

Consolidation: Patients in remission will receive high-dose cytarabine (days 1, 3, and 5) consolidation therapy for up to 3 cycles (except in the case of toxicity or receipt of stem cell transplant). Patients with core-binding factor (CBF) AML may receive 4 cycles of consolidation therapy. Therapy should be started as soon as possible (and within 14 days) after recovery from induction/re-induction therapy.

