10.3 Cytarabine

Product description: Antimetabolite. Commercially available in 100 mg, 500 mg, 1 gm, and 2 gm vials.

Solution preparation: For IV use, reconstitute the 100 mg vial with 5 mL bacteriostatic water for injection to achieve a concentration of 20 mg/mL. Add 10 mL of bacteriostatic water to the 500 mg vial to achieve a final concentration of 50 mg/mL. Add 10 and 20 mL of bacteriostatic water to the 1 and 2 gm vials respectively to achieve a final concentration of 100 mg/mL.

Storage and stability: The dry powder is stored at room temperature. Solutions reconstituted with sterile water without preservative should be used immediately; solutions reconstituted with Bacteriostatic of Water are stable up to 48 hours at controlled room temperature (15° to 30°C). Solutions with a slight haze should be discarded.

Route of administration: Continuous intravenous infusion over 24 hours.

Disposal: Care should be taken in disposing cytarabine. Dispose of per local regulations and the Wake Forest Hem/Onc Waste Disposal Guide.

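### Section 10.3 lists cytarabine only as a 24-hour infusion while 6.1 gives consolidation over 3 hours, and 10.3's diluent instruction makes no provision for the high-dose warning in 9.2

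*Combined protocol and SAP*

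**What the plan says.** **Route.** The pharmaceutical section for cytarabine (10.3) has a single route entry: "Continuous intravenous infusion over 24 hours". It names no treatment phase. The treatment table in 6.1 gives consolidation as "IV infusion over 3 hours, every 12 hours", on days 1, 3 and 5, with doses shown as "<60 yrs: 3,000 mg/m ² /day ≥ 60 yrs: 1,500 mg/m ² /day". The text of 6.1 adds: "Patients in remission will receive high-dose cytarabine (days 1, 3, and 5) consolidation therapy for up to 3 cycles". Patients with core-binding factor AML may have a fourth cycle.

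**Dose modification.** Section 7.0 has two renal steps for consolidation: a reduction to 1,000 mg/m² per dose, and a change to 400 mg/m²/day over 24 hours for 5 days.

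**Diluent.** The high-dose part of 9.2 says: "If high dose therapy is used, do not use a diluent containing benzyl alcohol". Section 10.3 directs bacteriostatic water for every vial size. For the smallest it says "reconstitute the 100 mg vial with 5 mL bacteriostatic water for injection to achieve a concentration of 20 mg/mL", it gives a like instruction for the 500 mg vial, and for the largest it says "Add 10 and 20 mL of bacteriostatic water to the 1 and 2 gm vials respectively to achieve a final concentration of 100 mg/mL". Preservative-free water appears only under storage: "Solutions reconstituted with sterile water without preservative should be used immediately".

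**The concern.** Someone preparing cytarabine would naturally turn to 10.3. As written, it gives a route that cannot be squared with the consolidation schedule in 6.1. It also gives a diluent instruction that does not mention the high-dose warning, which sits inside an adverse-event list in 9.2.

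Two things are at stake. One is whether consolidation is given as the treatment plan sets it out. The other, on an assumption the documents do not settle, is whether it could be prepared against the protocol's own safety warning. This is a point about consistent instructions and patient safety. No statistical quantity rests on it.

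**Working it through.** There is no plan figure to reproduce, so the check sets the sections side by side.

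**1. Route**

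| Source | Phase | Infusion time per treatment day |
|---|---|---|
| 10.3 | not limited | 24 h |
| 6.1 | induction and re-induction | infusion, duration not given in the table |
| 6.1 | consolidation | 2 x 3 h = 6 h |
| 7.0, second renal step | consolidation | 24 h |

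For induction, 10.3 is compatible with 6.1, which says it follows standard 7+3; section 1.0 describes the cytarabine in that regimen as a continuous infusion. For consolidation the sections conflict. Over the three treatment days of a cycle, 6.1 gives 3 x 6 = 18 infusion hours and 10.3 gives 3 x 24 = 72. A 24-hour infusion also cannot be repeated every 12 hours without overlap. The second renal step in 7.0 agrees with 10.3, but it is an exception and does not account for an unrestricted route entry.

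**2. Diluent**

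- The concentrations in 10.3 are arithmetically correct: 100 mg / 5 mL = 20 mg/mL; 500 mg / 10 mL = 50 mg/mL; 1 g / 10 mL and 2 g / 20 mL = 100 mg/mL.
- Section 9.2 restricts benzyl alcohol when high-dose therapy is used, and 6.1 uses the term high-dose for consolidation.
- Section 10.3 contrasts bacteriostatic water with water that has no preservative, so the former is preserved. No section names the preservative.
- If it is benzyl alcohol, 10.3 and 9.2 conflict for any dose the warning covers. If it is something else, they do not, but 10.3 still does not show the preparer that 9.2 has been met.

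**3. Which doses the warning reaches**

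Section 9.2 describes high-dose schedules as 2.0 to 3.0 g/m² every 12 hours for 12 doses. Consolidation in 6.1 has 3 days x 2 = 6 doses per cycle. Its doses are printed per day but scheduled every 12 hours, so both readings are shown:

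| Printed dose | If the daily total is split in two | If given at each infusion |
|---|---|---|
| 3,000 mg/m² | 1,500 mg/m², below the range | 3,000 mg/m², in the range |
| 1,500 mg/m² | 750 mg/m², below | 1,500 mg/m², below |

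The first renal step in 7.0 (1,000 mg/m² per dose) equals the 1 g/m² that 9.2 calls intermediate. On the label in 6.1, all consolidation is high-dose. On the range in 9.2, some or all of it is not.

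**4. Which vials matter**

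Assume a body surface of 1.5 to 2.2 m² (not in the documents). Induction at 100 mg/m²/day needs 150 to 220 mg per day. Two days' supply is 300 to 440 mg, still under one 500 mg vial. Consolidation, read per day as printed, needs 1,500 x 1.5 to 2.2 = 2,250 to 3,300 mg, or 3,000 x 1.5 to 2.2 = 4,500 to 6,600 mg. On that assumption the instruction for the 1 g and 2 g vials bears mainly on consolidation.

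**5. How many patients**

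Section 1.0 quotes a background remission rate of 60% to 70%, and the enrolment target is 40. 40 x 0.60 = 24 and 40 x 0.70 = 28. Each could have up to 3 cycles x 6 = 18 infusions, or 4 x 6 = 24 with core-binding factor disease.

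**The case against.** The strongest reply is that 6.1 is the operative dosing text and is explicit on duration and interval, while section 10 is product information on commercially available drugs. The warning in 9.2 is conditional and can be read as a specific exception to a general preparation text, and 10.3 does acknowledge preservative-free water. On that view only a cross-reference is missing.

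Part of this stands. Nothing shows that a preparer would follow 10.3 over 6.1, and the diluent texts can be read together. But the exception reading depends on the preparer finding one sentence in an adverse-event list to which 10.3 does not refer, and it leaves the route conflict untouched.

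Four stronger readings are tempting, and the documents do not support them:

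- *That 10.3 flatly contradicts 9.2 on diluent.* No section says bacteriostatic water contains benzyl alcohol.
- *That every consolidation dose is affected.* The 24-hour renal step in 7.0 agrees with 10.3 on route, and the reach of 9.2's warning over the lower doses is unclear.
- *That the plan expects 24 to 28 patients in consolidation.* The 60% to 70% is background in 1.0; section 13 sets no response assumption. Transplant in first remission (6.1.1) and the other reasons for ending treatment (6.5) would lower the count, as would drop-out, which 13.3 allows at up to 20% by 3 months.
- *That 10.3 is the text in error.* The documents show that the sections disagree, not which one is right.

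**Conclusion.** The route conflict holds on the text alone: for consolidation, 10.3 and 6.1 cannot both be followed, apart from the 24-hour renal step in 7.0. The diluent point is a real gap in 10.3. It becomes a conflict with 9.2 only if the bacteriostatic water is preserved with benzyl alcohol, and only for doses that the warning covers; both need an answer from outside these documents.

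The illustrative ceiling is about 24 to 28 of 40 patients entering consolidation, assuming the background remission rate applies and every patient in remission goes on to it. Sample size, power and the planned analyses are unaffected, and the infusion tracked for feasibility in 8.2 is induction daunorubicin. The point deserves correction because it concerns how a drug is prepared and given, and because correcting it is cheap.

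**What to change.** Reconcile 6.1, 7.0, 9.2 and 10.3 so that induction/re-induction and consolidation, including the renal modifications, each carry one consistent route and one consistent diluent instruction. Ask the study pharmacist to establish which preservative is in the bacteriostatic water used, and to confirm the reconciled wording. State which consolidation doses the high-dose warning in 9.2 is meant to cover, and place a cross-reference between 9.2 and 10.3. This review does not say which text is right and proposes no route, diluent or dose.

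The cost is a wording amendment to the treatment and pharmaceutical sections, best made before further consolidation doses are prepared. It changes no endpoint, analysis or sample size.

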9.3 Adverse Event Characteristics

- **CTCAE term (AE description) and grade:** The descriptions and grading scales found in the revised NCI Common Terminology Criteria for Adverse Events (CTCAE) version 4.0 will be utilized for AE reporting. All appropriate treatment areas should have access to a copy of the CTCAE version 4.0. A copy of the CTCAE version 4.0 can be downloaded from the CTEP web site (<http://ctep.cancer.gov>).
- **'Expectedness':** AEs can be 'Unexpected' or 'Expected' (see Section 7.1 above) for expedited reporting purposes only.
- **Attribution of the AE:**
 - Definite – The AE is **clearly related** to the study treatment.
 - Probable – The AE is **likely related** to the study treatment.
 - Possible – The AE **may be related** to the study treatment.
 - Unlikely – The AE is **doubtfully related** to the study treatment.
 - Unrelated – The AE is **clearly NOT related** to the study treatment.

9.4 STRC SAE Reporting Requirements

The Safety and Toxicity Reporting Committee (STRC) is responsible for reviewing SAEs for WFBCCC Institutional studies as outlined in Appendix B. STRC currently requires that all unexpected 4 and all grade 5 SAEs on these trials be reported to them for review. All WFBCCC Clinical Research Management (CRM) staff members assisting a Principal Investigator in investigating, documenting and reporting an SAE qualifying for STRC reporting are responsible for informing a clinical member of the STRC as well as the entire committee via the email notification procedure of the occurrence of an SAE.

9.5 WFUHS IRB AE Reporting Requirements

Any unanticipated problems involving risks to subjects or others and adverse events shall be promptly reported to the IRB, according to institutional policy. Reporting to the IRB is required regardless of the funding source, study sponsor, or whether the event involves an investigational or marketed drug, biologic or device. Reportable events are not limited to physical injury, but include psychological, economic and social harm. Reportable events may arise as a result of drugs, biological agents, devices, procedures or other interventions, or as a result of questionnaires, surveys, observations or other interactions with research subjects.

All members of the research team are responsible for the appropriate reporting to the IRB and other applicable parties of unanticipated problems involving risk to subjects or others. The Principal Investigator, however, is ultimately responsible for ensuring the

CYTARABINE PLUS CONTINUOUS INFUSION DAUNORUBICIN, WITH CARDIAC
MRI MONITORING, INDUCTION THERAPY FOR ADULTS WITH ACUTE MYELOID
LEUKEMIA; A FEASIBILITY STUDY

Wake Forest Baptist Comprehensive Cancer Center (WFCCC) CCCWFU 22616

prompt reporting of unanticipated problems involving risk to subjects or others to the IRB. The Principal Investigator is also responsible for ensuring that all reported unanticipated risks to subjects and others which they receive are reviewed to determine whether the report represents a change in the risks and/or benefits to study participants, and whether any changes in the informed consent, protocol or other study-related documents are required.

Any unanticipated problems involving risks to subjects or others occurring at a site where the study has been approved by the WFUHS IRB (internal events) must be reported to the WFUHS IRB within 7 calendar days of the investigator or other members of the study team becoming aware of the event.

Any unanticipated problems involving risks to subjects or others occurring at another site conducting the same study that has been approved by the WFUHS IRB (external events) must be reported to the WFUHS IRB within 7 calendar days of the investigator or other members of the study team becoming aware of the event.

Any event, incident, experience, or outcome that alters the risk versus potential benefit of the research and as a result warrants a substantive change in the research protocol or informed consent process/document in order to insure the safety, rights or welfare of research subjects.

10.0 Pharmaceutical Information

10.1 Pharmaceutical Accountability

The drugs used in this study regimen, daunorubicin and cytarabine, are commercially available.

10.2 Daunorubicin

Product description: Anthracycline. Commercially available in 20 mg and 50 mg glass vials of red colored lyophilized drug.

Solution preparation: Each 20 mg vial is reconstituted with 4 mL of sterile water to give a final concentration of 5 mg/mL.

Storage and stability: Intact vials are stored at room temperature and protected from direct sunlight. Reconstituted solutions are stable for 48 hours when refrigerated at 2°–8°C (36°–46°F) and 24 hours at room temperature, when protected from sunlight. Do not freeze.

Route of administration: Continuous intravenous infusion over 24 hours. Compatible with cytarabine. Incompatible with sodium heparin. Vesicant.

Disposal: Care should be taken in disposing daunorubicin. Daunorubicin is a vesicant; wear proper protective equipment when handling. Dispose of per local regulations and the Wake Forest Hem/Onc Waste Disposal Guide.

CYTARABINE PLUS CONTINUOUS INFUSION DAUNORUBICIN, WITH CARDIAC
MRI MONITORING, INDUCTION THERAPY FOR ADULTS WITH ACUTE MYELOID
LEUKEMIA; A FEASIBILITY STUDY

Wake Forest Baptist Comprehensive Cancer Center (WFBCCC) CCCWFU 22616

